### 9.3. Pharmacokinetic/Pharmacodynamic Evaluations

Decitabine plasma concentration-time models data will also be analyzed using a population PK approach (non-linear mixed effect models) to establish decitabine PK parameters (eg, clearance and volume of distribution). The population PK model proposed for the adult population will be updated with the data obtained in this patient population. Data from this study may be combined with data from other studies to perform the population PK analysis.

Analyses comparing PK parameters of  $C_{max}$  and AUC with PD endpoints of DNA methylation and gene expression profiling may be undertaken to explore any potential relationships.

## 9.4. Biomarkers

Biomarker analyses are dependent upon the availability of appropriate biomarker assays and may be deferred or not performed if, during or at the end of the trial, it becomes clear that the analysis will have no scientific value or if there are not enough samples or responders to allow for adequate biomarker evaluation. In the event that the trial is terminated early or shows poor clinical efficacy, completion of biomarker assessments will be based on justification and intended utility of the data. Biomarker sample collections will be prioritized in the manner specified in Section 9.6 in the event total blood volumes exceeds the EMA recommendations for pediatric trial related blood loss. Biomarker samples will not be stored for future research.

### 9.4.1. Pharmacodynamic Evaluations

DNA methylation and gene expression will be evaluated as potential pharmacodynamic biomarkers of the mechanism of action for DACOGEN and as response markers for treatment by the sequential administration of DACOGEN and cytarabine. This data will also be used to show biological activity across all ages enrolled in the study. Whole blood and/or bone marrow aspirates will be collected before study drug administration and according to the time and events schedule.

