- k) Bone marrow aspirates will be performed at the end of Cycle 1 of sequential treatment (Day 28 or within 8 days of the start of the next cycle), the end of Cycle 2 if the subject did not achieve a CR at the end on Cycle 1, at the end of sequential treatment, or at any time disease progression is suspected. For Phase 1, bone marrow aspirates at end of Cycle 1 should be obtained no later than Day 42 in order to determine potential dose limiting toxicity. If available, a portion of the bone marrow aspirate collected at Screening and at end of the first Cycle will be used for DNA methylation/ mutation assessment, gene expression, and micro RNA analyses.
- l) Results should be recorded if a bone marrow aspirate is obtained as part of standard clinical care.

- m) Response assessment is performed at time at which bone marrow aspirate is obtained.
- n) Hemoglobin, platelet count, white blood cell count, absolute neutrophil count (ANC), peripheral blast count
- o) First cycle only
- p) For the DACOGEN continuation period, hematology samples are obtained on Day 1 of each cycle prior to drug administration.
- q) To include  $\text{Na}^+$ ,  $\text{K}^+$ , creatinine, aspartate aminotransferase (AST), alanine aminotransferase (ALT), total bilirubin, serum uric acid
- r) 0.5 mL whole blood to be obtained (blood should not be collected through the same line through which decitabine is infused, see Section 9.2.3) at; pre-infusion, 0.5 h during infusion, end of infusion, +5 min, +0.5h, +1h, and +2h after end infusion. Samples will be collected from Phase 1 and Phase 2 subjects. 0.5 ml of cerebrospinal fluid (CSF) will be collected for PK analysis when/if CSF is obtained as part of routine medical care except at screening.
- s) Whole blood sample (2 mL) for DNA methylation pattern and DNA mutation determination at screening, prior to drug administration on Day, 8, and at the end of Cycle 1. This sample may also be used for gene expression and micro RNA analysis in the event only one biomarker blood sample can be drawn.
- t) Whole blood (2.5 mL) for gene expression profiling and micro RNA analysis at screening, prior to drug administration on Day 8, and at the end of Cycle 1.

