## 8. PRESTUDY AND CONCOMITANT THERAPY

All prior therapies for AML must be recorded. CNS-directed intrathecal therapy administered within 30 days before the first dose of study drugs must be recorded.

Prophylactic intrathecal therapy and hydroxyurea are allowed until 1 day prior to Cycle 1 Day 1.

Concomitant therapies must be recorded throughout the study beginning with start of the first dose of study drug to 30 days after the last dose of study drug.

Concomitant therapies allowed under this protocol are:

- Packed red blood cell transfusion: transfusions may be given as clinically indicated
- Platelet transfusion: to be administered when platelets are  $<10,000/\mu L$  or according to institutional standards.
- Prophylactic antibiotics will be administered according to institutional standards.
- Management of febrile neutropenia should be in accordance with institutional standard:

Febrile neutropenia is defined as a body temperature of at least:

38.5°C on 1 occasion or 38°C on 2 occasions when the ANC is  $<1000/\mu L$ . Febrile patients are to be evaluated by physical exam, complete blood count (CBC) with differential, and blood culture. Patients with febrile neutropenia or suspected sepsis on the basis of physical exam are to be hospitalized for appropriate broad-spectrum antibiotic coverage, consistent with local pathogen sensitivities.

- Anti-emetics and other agents needed for supportive care may be given in accordance with institutional treatment standards
- Any other medications required for clinical management of the patient
- Other than the study agents, patients cannot receive other anticancer chemotherapy during this study.

The sponsor must be notified in advance (or as soon as possible thereafter) of any instances in which prohibited therapies (eg, other anticancer medications) are administered.

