### 9.1.2. Screening Phase

The signed ICF/assent must be obtained before any study-specific procedures are performed. The Screening Phase begins when the first study-specific screening assessment is conducted. During the Screening Phase, eligibility criteria will be reviewed and a complete clinical evaluation will be performed. Screening procedures will be performed up to 14 days before Cycle 1 Day 1; however, results of tests such as radiologic tests, bone marrow collection for morphology, cytogenetics, and either immunohistochemistry or immunofluorescence performed up to 28 days before Cycle 1 Day 1 as routine work-up for the subject's disease can be used. Cardiac function must be normal, defined as shortening fraction of  $\geq 29\%$  by echocardiogram or LVEF  $> 58\%$ . Results obtained prior the screening period are acceptable provided no potentially cardiotoxic therapy was provided between that evaluation and the first dose of decitabine (Cycle 1 day 1). A negative pregnancy test for females of childbearing potential must be documented within 7 days before the Cycle 1 Day 1 dosing. If a pregnancy test result is more than 7 days old at Cycle 1 Day 1, then the test must be repeated locally and documented.

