## **11.7. Biomarker Analyses**

Biomarker analyses will be performed and stratified by clinical covariates or molecular subgroups using appropriate statistical methods. When too few data are available for statistical analyses, data will be summarized with descriptive statistics and/or visualized.

Pharmacodynamic biomarker results from Phase 1 and 2 will be summarized with descriptive statistics and/or visualized for each dose level. Changes in the values of individual biomarkers from baseline to selected time points will be summarized by dose cohort.

Correlation of baseline values or changes in biomarker values with response or time-to-event endpoints will identify responsive (or resistant) subgroups of patients as well as genes and pathways affected by DACOGEN treatment.

Planned biomarker analyses are dependent upon the availability of appropriate biomarker assays and may be deferred if emerging study data show no likelihood of providing useful scientific information.

Results of biomarker analyses will be presented in a separate report.

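### The only pre-drug biomarker blood is drawn at screening, up to 14 days before the first DACOGEN dose, so the change to Day 8 is confounded by an untreated gap that varies by child

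*Combined protocol and SAP*

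**What the plan says.** - Section 9.4.1, with the same sentence in Sections 9.4.2 to 9.4.4: "Whole blood and/or bone marrow aspirates will be collected before study drug administration and according to the time and events schedule". A screening draw satisfies this.
- Time and Events Schedule, footnote s, on the 2 mL tube: "for DNA methylation pattern and DNA mutation determination at screening, prior to drug administration on Day, 8, and at the end of Cycle 1". Footnote t, on the other tube: "Whole blood (2.5 mL) for gene expression profiling and micro RNA analysis at screening, prior to drug administration on Day 8", and again at the end of Cycle 1. The schedule has hematology and chemistry on Day 1 but no biomarker blood.
- Section 9.1.2: "Screening procedures will be performed up to 14 days before Cycle 1 Day 1".
- Section 8: "Prophylactic intrathecal therapy and hydroxyurea are allowed until 1 day prior to Cycle 1 Day 1".
- Section 6.3: DACOGEN is given on Days 1 to 5 and cytarabine on Days 8 to 12.
- Section 11.7: "Changes in the values of individual biomarkers from baseline to selected time points will be summarized by dose cohort". Baseline is not defined there. Section 11 leaves details to the SAP, and nothing in the combined document supplies that definition.
- Section 9.4.1 treats methylation and expression as candidate pharmacodynamic markers of DACOGEN's mechanism and expects them to demonstrate activity at every age enrolled. Section 11.7 expects correlations of biomarker changes with outcome to reveal the genes and pathways that DACOGEN affects.

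**The concern.** Day 8 is the one time point at which DACOGEN has been given and cytarabine has not, so a DACOGEN effect has to be read from the change up to that sample. Its comparator may be two weeks old by the first infusion. During that time the leukemia is untreated by study drug and may be changing, and hydroxyurea or intrathecal drugs may be given. The samples are whole blood and no cell sorting is described, so a shift in the proportion of blasts could by itself move the measured profile.

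Nothing else in the design separates drug effect from drift. There is no control arm. The dose cohorts differ only in cytarabine, which has not started when the Day 8 sample is taken, so comparing cohorts does not help at that point. Phase 1 cohorts have 2 to 6 children, too few to average out a gap that differs from child to child. At stake is whether the research blood answers the pharmacodynamic question for which it is drawn.

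**Working it through.** **1. Number of draws (Table 4).** Hematology 18 × 2 = 36; chemistry 7 × 2 = 14; PK 7 × 0.5 = 3.5; pharmacodynamic 3 × 2 = 6; biomarkers 3 × 2.5 = 7.5; cytogenetics 1 × 2 = 2. The sum is 69 mL, which reproduces the stated total. Three tubes of each biomarker type match screening, Day 8 and end of Cycle 1, leaving none for Day 1.

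**2. Untreated share of the interval.** Let g be the days from the screening draw to Day 1. Day 1 to Day 8 is 7 days, so the interval is g + 7 and the untreated share of days is g/(g + 7).

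| g (days) | Interval (days) | Untreated share |
|---|---|---|
| 0 | 7 | 0% |
| 3 | 10 | 30.0% |
| 7 | 14 | 50.0% |
| 10 | 17 | 58.8% |
| 14 | 21 | 66.7% |

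If the schedule's numbering (Day -14 to 0) is counted with a Day 0, the maximum is 15/22 = 68.2%. The share passes one half only when the draw is more than 7 days before Day 1.

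The documents give no distribution of g. Assuming draws spread evenly over 0 to 14 days, 7 of 15 possible values (47%) exceed 7 days and the mean share is 44%. Over 1 to 14 days the figures are 50% and 47%. The limits are 0% if every draw is on Day 1 and 66.7% if every draw is 14 days before.

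**3. Effect of moving both tubes to Day 1 before dosing.** g becomes 0, the interval 7 days and the untreated share 0%. The number of tubes and the 69 mL total do not change.

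**4. Single-draw limit (Section 9.6: 0.8 to 0.9 mL/kg).** Table 4 volumes, all tubes counted as study blood.

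| Draw | Volume (mL) | Minimum weight (kg) |
|---|---|---|
| Screening now, all tubes at once: 2 + 2 + 2 + 2 + 2.5 | 10.5 | 11.7–13.1 |
| Screening after the move: 2 + 2 + 2 | 6.0 | 6.7–7.5 |
| Day 1 after the move: 2 + 2 + 2 + 2.5 | 8.5 | 9.4–10.6 |
| Day 1 after the move, single 2 mL tube: 2 + 2 + 2 | 6.0 | 6.7–7.5 |

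**5. Four-week limit (Section 9.6: 2.4 to 2.7 mL/kg).**
- After the move, Days 1 to 28: Day 1 8.5 + Day 5 5.5 (hematology 2, PK 3.5) + Day 8 6.5 + Day 22 2 + Day 28 6.5 = 29.0 mL, needing 10.7–12.1 kg.
- Now, screened on Day -5: 10.5 + Day 1 4 + 5.5 + 6.5 + 2 = 28.5 mL in 28 days, needing 10.6–11.9 kg.
- Now, screened on Day -14: 10.5 + 4 + 5.5 + 6.5 = 26.5 mL, needing 9.8–11.0 kg.

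**The case against.** **The share of days is not the share of the measured change.** A reader might infer that most of the Day 8 change could be untreated time and hydroxyurea. The documents do not support that. All five DACOGEN doses precede the Day 8 sample, and Section 1.1.3.1 reports maximal in vitro inhibition of methylation after 5 days. No drift rate, blast doubling time or hydroxyurea effect on blood methylation or expression is given. This part of the objection stands.

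**The aim is exploratory.** Section 9.2.2 sets out to explore these effects, Section 11.7 plans descriptive summaries and some stratification by clinical covariates, and Section 9.4 allows the analyses to be deferred or dropped. This stands and limits the weight of the point. It does not make the comparator right.

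**A Day 1 baseline is not clean either.** Hydroxyurea may run up to the day before, so its withdrawal would fall between Day 1 and Day 8, and a week of disease change remains. This stands: the move reduces the confounding without removing it.

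**The blood-volume gain is partial.** Screening tubes can be split over 14 days, while Day 1 tubes cannot. Table 4 also allows volumes to be adjusted for children. This stands. The four-week objection is minor: a child screened on about Day -5 already reaches 28.5 mL, against 29.0 mL after the move.

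**Sites may draw close to Day 1 anyway.** They may, but nothing requires it.

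A reader might also infer a 28-day-old baseline, because Section 9.1.2 accepts certain results "performed up to 28 days before Cycle 1 Day 1 as routine work-up". That allowance concerns routine disease work-up and does not name the biomarker blood.

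**Conclusion.** The point holds as a flaw in the timing of the comparator. The change to Day 8 includes 0 to 14 pre-treatment days, varying by child, in which cytoreductive and intrathecal therapy is permitted. At the maximum, 14 of 21 days precede DACOGEN. Sections 9.4.1 and 11.7 attribute the change to the drug, and the plan specifies no adjustment for the gap or for hydroxyurea.

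The figures are for elapsed time and rest on the 14-day window in Section 9.1.2. The size of any bias in methylation or expression is unknown. The consequence is confined to the exploratory pharmacodynamic analyses. DLT and MTD, decitabine PK and the CR + CRi rate do not use this baseline.

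**What to change.** - In the schedule and footnotes s and t, move the baseline 2 mL and 2.5 mL blood tubes from screening to Cycle 1 Day 1 before the first DACOGEN infusion, or within the preceding 24 hours, together with the Day 1 hematology. Each baseline then has a peripheral blast count taken with it.
- In Section 11.7, define this sample as baseline for every blood biomarker change. It is still a pre-treatment sample, so it also serves mutation and predictive profiling. Leave the screening marrow portion as it is.
- Record pre-study hydroxyurea use and the draw date in the analysis data, and report both with the Day 8 change. Section 9.6 already requires collection dates on the requisition form, and Section 8 requires prior AML therapy to be recorded, so little new collection is needed.
- For children too small for an 8.5 mL draw, apply the Section 9.6 priority order and the single-tube option in footnote s, or allow the baseline tube at screening with the gap reported.

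Cost: a change to the schedule, its footnotes and Section 11.7, with the total still at 69 mL. Children who fail screening no longer give 4.5 mL of research blood. The kit must be ready before the first infusion, the Day 1 draw cannot be spread over several days, and Days 1 to 28 come to about 29 mL at Table 4 volumes.

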### 9.4.2. Gene Expression Profiling

Gene expression profiling (GEP) may be evaluated in RNA for gene signatures predictive of response to DACOGEN. The expression of single genes such as estrogen receptor and p15INK4B may be examined in relation to response using RTqPCR. Whole blood and/or bone marrow aspirates will be collected before study drug administration and according to the time and events schedule.

### 9.4.3. Gene Methylation Profiling

Gene methylation profiling will be evaluated in DNA as a predictor of response to treatment by the sequential administration of DACOGEN and cytarabine. The following genes will be highlighted for determination of efficacy: CDH1, CDH13, ER, NR4A3, NPM2, OLIG2, p15INK4B, PGRA, PGRB, RIL. Additional genes may be analyzed or global profiling may be applied as necessary. Whole blood and/or bone marrow aspirates will be collected before study drug administration and according to the time and events schedule.

### 9.4.4. Gene Mutation Profiling

Gene mutations in DNMT3a and NPM1 among others plus other genetic mutations relating to drug response or disease, such as FLT3, IDH1, IDH2, TET2 and CEBPA, MLL-PTD, c-KIT, WT1, PTPN11 will be evaluated for prediction of response to treatment by the sequential administration of DACOGEN and cytarabine in DNA obtained from whole blood and/or bone marrow aspirate. Whole blood and/or bone marrow aspirates will be collected before study drug administration and according to the time and events schedule.

#### 9.4.5. MicroRNA Analysis

miR29b may be evaluated for prediction of response to treatment by the sequential administration of DACOGEN and cytarabine in microRNA obtained from whole blood and/or bone marrow aspirate.

#### 9.5. Safety Evaluations

The evaluation period for safety will start from the time a signed consent/assent is provided. Toxicity/safety will be determined using National Cancer Institute common terminology criteria for adverse events (NCI-CTCAE) version 4.0.

The primary expected toxicity of cytarabine is severe myelosuppression. In addition rare cases of hypersensitivity and anaphylaxis have been reported after cytarabine dosing as well as “sudden respiratory arrest syndrome” occurring 6 to 12 hours after dosing and tumor lysis syndrome.

In addition to myelosuppression, administration of DACOGEN can cause peripheral edema, pallor, cardiac murmur and hypotension. Fever, fatigue, headache, lethargy and other CNS symptoms may occur. Cough, dyspnea, pneumonia and pharyngitis may be seen as well as mucositis and other side effects associated with myelosuppression and cellular cytotoxicity.

For the purposes of DLT evaluation, Cycle 1 will last until the start of Cycle 2, unless there is no recovery from toxicity within the specified time.

During the conduct of Phase 1 the SET will evaluate the tolerability of the combination until such times as a MTD for cytarabine can be agreed upon. Details regarding the SET are provided in Section 11.9.

During Phase 1, blood counts are to be monitored, but hematological parameters are not used to determine the MTD (ie, low blood counts per se are not considered to be dose-limiting toxicities or serious adverse events) because peripheral blood counts and bone marrow function are compromised in patients with relapsed leukemia. Hematological toxicity will only be assessed in responding patients who have grade 4 neutropenia ( $<0.5 \times 10^9/L$ ) or grade 4 thrombocytopenia ( $<25 \times 10^9/L$ ) due to a hypoplastic marrow at Day 42, in the absence of leukaemia.

During Phase 2 only myelosuppression events that are considered life threatening or result in an admission to hospital would be considered as serious adverse events.

Safety will be measured by adverse events, laboratory test results, vital sign measurements, physical examination findings, and assessment of performance status. Any clinically relevant changes occurring during the study must be recorded on the Adverse Event section of the eCRF. Any clinically significant abnormalities persisting at the end of the study/early withdrawal will be followed by the investigator until resolution or until a clinically stable endpoint is reached. The study will include the following evaluations of safety and tolerability according to the time points provided in the Time and Events Schedule.

Any of the safety monitoring assessments may be performed more frequently, and adverse events should be evaluated by the investigator according to standard practice, and if clinically indicated.

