### **Serious Adverse Event**

A serious adverse event based on ICH and EU Guidelines on Pharmacovigilance for Medicinal Products for Human Use is any untoward medical occurrence that at any dose:

- Results in death
- Is life-threatening  
(The subject was at risk of death at the time of the event. It does not refer to an event that hypothetically might have caused death if it were more severe.)
- Requires inpatient hospitalization or prolongation of existing hospitalization
- Results in persistent or significant disability/incapacity
- Is a congenital anomaly/birth defect
- Is a suspected transmission of any infectious agent via a medicinal product
- Is Medically Important\*

\*Medical and scientific judgment should be exercised in deciding whether expedited reporting is also appropriate in other situations, such as important medical events that may not be immediately life threatening or result in death or hospitalization but may jeopardize the subject or may require intervention to prevent one of the other outcomes listed in the definition above. These should usually be considered serious.

If a serious and unexpected adverse event occurs for which there is evidence suggesting a causal relationship between the study drug and the event (eg, death from anaphylaxis), the event must be reported as a serious and unexpected suspected adverse reaction even if it is a component of the study endpoint (eg, all-cause mortality).

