**12.2. Procedures****12.2.1. All Adverse Events**

All adverse events and special reporting situations, whether serious or non-serious, will be reported from the time a signed and dated ICF is obtained until 30 days after the last dose of study drug. Serious adverse events, including those spontaneously reported to the investigator

within 30 days after the last dose of study drug, must be reported using the Serious Adverse Event Form. The sponsor will evaluate any safety information that is spontaneously reported by an investigator beyond the time frame specified in the protocol.

All events that meet the definition of a serious adverse event will be reported as serious adverse events, regardless of whether they are protocol-specific assessments.

All adverse events, regardless of seriousness, severity, or presumed relationship to study drug, must be recorded using medical terminology in the source document and the eCRF. Whenever possible, diagnoses should be given when signs and symptoms are due to a common etiology (eg, cough, runny nose, sneezing, sore throat, and head congestion should be reported as "upper respiratory infection"). Investigators must record in the eCRF their opinion concerning the relationship of the adverse event to study therapy. All measures required for adverse event management must be recorded in the source document and reported according to sponsor instructions.

The sponsor assumes responsibility for appropriate reporting of adverse events to the regulatory authorities. The sponsor will also report to the investigator (and the head of the investigational institute where required) all serious adverse events that are unlisted (unexpected) and associated with the use of the study drug. The investigator (or sponsor where required) must report these events to the appropriate Independent Ethics Committee/Institutional Review Board (IEC/IRB) that approved the protocol unless otherwise required and documented by the IEC/IRB.

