- It becomes unlikely that any additional information can be obtained (subject or health care practitioner refusal to provide additional information, lost to follow-up after demonstration of due diligence with follow-up efforts)

Suspected transmission of an infectious agent by a medicinal product will be reported as a serious adverse event. Any event requiring hospitalization (or prolongation of hospitalization) that occurs during the course of a subject's participation in a study must be reported as a serious adverse event, except hospitalizations for the following:

- Administration of study drugs
- Hospitalizations not intended to treat an acute illness or adverse event (eg, social reasons such as pending placement in long-term care facility)

- Surgery or procedure planned before entry into the study (must be documented in the eCRF). Note: Hospitalizations that were planned before the signing of the ICF, and where the underlying condition for which the hospitalization was planned has not worsened, will not be considered serious adverse events. Any adverse event that results in a prolongation of the originally planned hospitalization is to be reported as a new serious adverse event.
- For convenience the investigator may choose to hospitalize the subject for the duration of the treatment period.

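### Section 9.5 sets a narrower test for serious myelosuppression in Phase 2 than Section 12, chiefly by leaving out prolonged hospital stay and medical importance, and the protocol does not say which section prevails.

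*Combined protocol and SAP*

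**What the plan says.** Section 9.5 gives a rule for each phase. For Phase 1 it explains that "low blood counts per se are not considered to be dose-limiting toxicities or serious adverse events", because counts and marrow function are already compromised in relapsed leukemia. For Phase 2 it says "During Phase 2 only myelosuppression events that are considered life threatening or result in an admission to hospital would be considered as serious adverse events".

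Sections 12.1.1 and 12.2.2 each give the general SAE definition. Besides life-threatening events, the list includes "Results in death", "Requires inpatient hospitalization or prolongation of existing hospitalization", "Results in persistent or significant disability/incapacity" and "Is Medically Important". Section 12.2.1 adds that "All events that meet the definition of a serious adverse event will be reported as serious adverse events".

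Section 12.2.2 repeats that an event requiring hospitalization or prolonging it must be reported as serious, and then lists excepted hospitalizations. One of these reads "For convenience the investigator may choose to hospitalize the subject for the duration of the treatment period". A note under another exception says that an adverse event extending an originally planned stay is a new SAE. Section 12.2.3 removes disease progression as an event term. Neither list of exceptions mentions myelosuppression.

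**The concern.** Section 9.5 introduces its two conditions with the word *only*, so it works as a restriction and not as a set of examples. Section 12 applies its full list to every event. A site reading Section 9.5 and a site reading Section 12 could therefore reach different answers about the same child.

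Section 9.5 names severe myelosuppression as the primary expected toxicity of cytarabine, and the safety profile is a secondary objective (Section 2.1). SAE status starts the 24-hour reporting clock in Section 12.2.2, and under Section 11.8 it can lead to listings or narratives. Section 3.1.2 says there is no independent data monitoring committee, so consistent SAE classification across sites carries some weight.

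**Working it through.** There is no figure to reproduce. The check sets the two rules side by side.

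| Criterion in Sections 12.1.1 and 12.2.2 | In the Section 9.5 Phase 2 sentence? | Does the difference matter for myelosuppression? |
|---|---|---|
| Death | Not named | Hardly: a fatal event has normally met the life-threatening test first |
| Life threatening | Yes | No difference |
| Inpatient hospitalization | Yes, as admission | No difference |
| Prolongation of existing hospitalization | Not named | Yes, for subjects already in hospital |
| Persistent or significant disability | Not named | Possible |
| Congenital anomaly | Not named | Little relevance |
| Suspected transmission of an infectious agent | Not named | Little relevance |
| Medically important | Not named | Yes |

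The differences with practical weight are prolongation and medical importance, with disability as a lesser one.

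Next, apply both rules to three cases of Phase 2 cytopenia, none judged life threatening.

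1. *Child at home, admitted because of the event.* Section 9.5: serious, through admission. Section 12: serious. The sections agree.
2. *Child already in hospital under the convenience provision, whose stay is extended by the event.* Section 9.5: not serious, because no admission results. Section 12: serious, through prolongation. The sections conflict.
3. *Child at home, not admitted, event judged medically important.* Section 9.5: not serious. Section 12: serious. The sections conflict.

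Cases 1 and 2 can involve the same toxicity at the same grade. They differ only in whether the site was already keeping the child in hospital.

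The number of subjects in cases 2 and 3 would need three inputs: how many children treated under the Phase 2 rule have such events; what share are inpatients at the time; and, among these, how often the stay is extended without a threat to life (for case 3, how often the event is judged medically important). The documents give none of these for this population and regimen.

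**The case against.** The strongest reply is that Section 12 already settles the matter. Section 12.2.1 requires every qualifying event to be reported, Section 12.2.2 says prolongation must be reported, and the adverse event paragraph in Section 9.5 itself refers to Section 12 for follow-up. A site that follows Section 12 loses nothing. This stands as a limit: the defect is two conflicting instructions, not proven under-reporting. It does not remove the conflict, because the Section 9.5 sentence is specific to this toxicity and phase, and nothing withdraws it.

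The sentence might also be parsed as applying *in Phase 2 only*, without restricting the criteria. The Phase 1 text just before it, which explains why low counts are not serious, favors the restrictive reading. On either parsing the wording needs clarifying.

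Its reach is uncertain too. Section 1.1.4.2.2 separates myelosuppression (the cytopenias) from its consequences, such as infection and bleeding. On that vocabulary Section 9.5 may govern only the cytopenias. Where febrile neutropenia falls is not stated. This narrows the point.

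Finally, the effect on analysis is small. Section 12.2.1 has all adverse events recorded whatever their seriousness, Section 12.1.3 grades them by CTCAE, and Section 11.8 summarizes treatment-emergent events by percentage of subjects. Summaries or listings of serious events are only optional there. This stands, and it is why the severity is minor.

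**Conclusion.** The Phase 2 sentence in Section 9.5 is wrong as written: read literally, it contradicts Sections 12.1.1, 12.2.1 and 12.2.2, and no precedence is stated. Severity is minor. SAE classification, 24-hour reporting and any SAE summaries could vary by site. The primary endpoint, the sample size and the summaries of all adverse events are unaffected. The conclusion assumes the restrictive reading of *only*, and its practical importance depends on some subjects being inpatients when the event occurs.

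The documents do not support three stronger inferences.

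- *Fatal events are dropped.* Section 12.1.1 defines life threatening as being at risk of death at the time of the event. A fatal myelosuppression event has normally met that test and stays serious under Section 9.5.
- *The number of misclassified subjects can be read off by applying the 34% febrile neutropenia rate in Table 2 to the 17 Phase 2 subjects in Section 11.2.* The 17 include subjects treated at the MTD in Phase 1, of whom Section 3.1.1 allows up to 6, so as few as 17 − 6 = 11 may be newly enrolled. The 34% comes from older adults on single-agent DACOGEN. Febrile neutropenia may fall outside the sentence, and the share of subjects already in hospital is not given.
- *Pooled Phase 1 and Phase 2 summaries necessarily mix rules.* The Phase 1 text excludes only low counts by themselves, which is compatible with Section 12. The Phase 2 sentence may have been meant to express the same idea.

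**What to change.** Reconcile the sections by replacing the Phase 2 sentence in Section 9.5 with one that covers both phases, for example: *In both phases, a myelosuppression event is serious when it meets any criterion in Section 12.1.1; low blood counts that meet none of those criteria are not serious adverse events.* This keeps the evident purpose of Section 9.5, which is to avoid SAE reports for routine cytopenias, and makes the classification independent of whether a site keeps children in hospital. It changes event classification only and leaves treatment untouched.

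The cost is one sentence, with possibly a few more SAE reports for prolonged stays and medically important events.
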